#### Culture Conversion

Culture conversion is defined as MAC culture negative at 2 consecutive visits during the treatment period. The conversion status will be reversed by a positive culture after conversion (recurrence). As such, a subject may achieve culture conversion multiple times during the study. The date of conversion is defined by the date of the first of 2 consecutive negative cultures.

The secondary endpoint culture conversion by Month 6 is defined as MAC culture negative at Month 5 and Month 6 with the adjustment for non-productive sputum (described below) and additional rules described in [Section 9.3.1.2.1](#).

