#### Non-productive sputum assessments

If a subject is unable to produce sputum spontaneously, sputum may be induced. If after induction, a subject is still unable to produce sputum despite reasonable efforts, this will be recorded as non-productive at that timepoint.

A non-productive assessment will be considered culture positive if the assessment occurs prior to culture conversion or post recurrence. A non-productive assessment will be considered culture negative if the assessment occurs post culture conversion.

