#### Categorical Analysis

The following categories for change from baseline will be defined:

- Very much better if change from baseline = -4
- Much better if change from baseline = -3
- Better if change from baseline = -2
- Somewhat better if change from baseline = -1
- No changed if change from baseline = 0
- Somewhat worse if change from baseline = 1
- Worse if change from baseline = 2
- Much worse if change from baseline = 3
- Very much worse if change from baseline = 4

In addition, the following simplified categories for change from baseline will be defined:

- Improved (Very much better / Much better / Better / Somewhat better) if change from baseline  $\leq -1$
- No change if change from baseline = 0
- Worse (Very much worse / Much worse / Worse / Somewhat worse) if change from baseline  $\geq 1$

Within-subject change from baseline to Month 7 are summarized as follows:

- Proportion of subjects in each PGI-S category for change from baseline to Month 7.
- Proportion of subjects in each PGI-S simplified category (Improved/No change/Worsen) for change from baseline to Month 7 ( $\leq -1$ , 0,  $\geq 1$ ) by treatment group and pooled.
- Between treatment groups comparison of the proportion of subjects in PGI-S Improved simplified category (i.e., change from baseline to Month 7  $\leq -1$ ) using Cochran-Mantel-Haenszel test stratified by history of MAC lung infection (initial or subsequent).

For the purpose of this analysis, PRO data for subjects with missing data, imputations of change from baseline values will be averaged across 50 available imputations and rounded to the nearest integer to obtain a single value per subject.

### 11.3. Culture Conversion by Month 7

The endpoint of interest is the proportion of subjects achieving culture conversion by Month 7. The reporting will be presented based on the ITT analysis set and will be provided by randomized treatment group.

Converters by Month 7 are subjects who have a negative culture at Month 7, and have achieved culture conversion by one of the following:

- MAC culture negative at Month 6 after adjustment for non-productive sputum, or
- Missing MAC culture at Month 6, and one of the below:
  - Achieved culture conversion (2 consecutive monthly negative sputum cultures), have negative culture after conversion, do not have recurrence after conversion, with at most 1 missing sputum assessment at or before Month 5, or
  - Negative culture at Month 5

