Non-converters by Month 7 are subjects who satisfy one of the following criteria:

- Die after randomization, or
- Have a positive MAC culture at Month 6 and/or Month 7 (after adjustment for non-productive)

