### 11.3.1.1. Data Handling

For the purpose of the analysis the influence of ICEs ([Section 7.5](#)) and the presence of the missing data on the estimation of culture conversion proportion by Month 7 will be taken into consideration.

Culture conversion by Month 7 will be handled by following rules:

1. Derive culture conversion by Month 7 using the rules above. Retrieved sputum assessments will be used in the analysis, ie, collected after early termination of ALIS/ELC (see [Section 7.4](#) for definition)
2. Data for subjects who complete 6 months of the randomized treatment however conversion status by Month 7 is not available will be imputed based on the observed status distribution from the subjects who completed 6 months of randomized treatment (ALIS/ELC, AZI, and ETH), have Month 7 conversion status determined, and were randomized to the same treatment group. This approach is consistent with MAR approach imputation.
3. When retrieved assessments are unavailable or #1 does not provide conversion status by Month 7, the missing Month 7 conversion status will be imputed as follows:
  - For subjects experiencing ICE (other than death), their missing Month 7 conversion status will be imputed based on the retrieved Month 7 conversion distribution from the subjects experiencing ICE (retrievers). MNAR imputation of the data for those subjects experiencing ICE is applied.
  - For subjects not experiencing ICE, their missing Month 7 conversion status will be imputed based on the observed status distribution from the subjects who completed 6 months of randomized treatment, have Month 7 conversion status determined, and were randomized to the same treatment group. This approach is consistent with MAR approach imputation.

The ELC treatment group (including retriever) will be used instead if the ICE retriever subgroup is too small to allow imputations as described above. The decision as to which group will be used in the imputation will be determined prior to unblinding at the blinded data review meeting.

Imputation details are included in the [Appendix I](#).

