The missing data will be multiply imputed using PROC MI in SAS. Fifty replications are sufficient to reflect variability of the imputations. Logistic regression will be used in the MI procedure with model factors including randomization stratum (history of MAC lung infection, initial or subsequent) and randomized treatment group.

[REDACTED]

Imputations for subjects whose Month 6 conversion status is unavailable and who discontinued ALIS/ELC early due to a non-ICE event:

For subjects not experiencing ICE, their missing Month 6 conversion status will be imputed based on the observed data distribution (flagged as Ref\_MAR) from the subjects who completed 6 months of randomized therapy, have Month 6 conversion status available, and are randomized to the same treatment group. This approach is consistent with MAR approach.

The missing data will be multiply imputed using PROC MI in SAS. Fifty replications are sufficient to reflect variability of the imputations. Logistic regression

will be used in the MI procedure with model factor randomization stratum (history of MAC lung infection, initial or subsequent).

Imputations for subjects completing randomized therapy and whose conversion status at Month 6 is unavailable

Data for subjects who complete 6 months of the randomized treatment however Month 6 conversion status is not available will be imputed based on the observed distribution from the subjects who completed 6 months of randomized treatment, have Month 6 conversion status available, and were randomized to the same treatment group. This approach is consistent with MAR approach imputation. The missing data will be multiply imputed using PROC MI in SAS as described above.

Analysis methods

Following each round of imputation, a full set of subject's conversion status at Month 6 will be created by combining the observed values and sets of imputed values under the MNAR and MAR assumptions. This process will result in a total of 50 full sets.

The analysis as specified in Section 9.3.1.2 will be performed using each of the 50 full sets. The 50 sets of results will be then combined using Rubin's rule implemented via SAS PROC MIANALYZE with the specification of their effect estimates together with the corresponding standard errors, resulting in a single set of estimates and testing statistics for the treatment effect.

Imputation of conversion status by Month 7

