The multiple imputation of culture conversion status by Month 7 follows the same approach as the imputation of culture conversion by Month 6 described above. Model will additionally include culture conversion status by Month 6 (possibly imputed) as additional model factor.

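### The Month 7 conversion imputation pools subjects with a negative Month 6 culture but no conversion by Month 6 with Month 6 positive subjects, who are non-converters by rule

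*SAP*

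**What the plan says.** SAP Section 9.3.1.1 sets the Month 6 endpoint: "The secondary endpoint culture conversion by Month 6 is defined as MAC culture negative at Month 5 and Month 6". Its paragraph on non-productive sputum adds: "A non-productive assessment will be considered culture positive if the assessment occurs prior to culture conversion or post recurrence".

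SAP Section 11.3 sets the Month 7 endpoint. On the positive side: "Converters by Month 7 are subjects who have a negative culture at Month 7, and have achieved culture conversion by one of the following". The first route listed is a negative Month 6 culture. On the negative side, apart from death, the criterion is "Have a positive MAC culture at Month 6 and/or Month 7 (after adjustment for non-productive".

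Subjects who meet neither definition are imputed under Section 11.3.1.1. For those who complete treatment, and for those who stop ALIS/ELC without an intercurrent event (ICE), the reference set is same-arm completers who "have Month 7 conversion status determined, and were randomized to the same treatment group". For those with an ICE, it is the retrievers with an ICE. If those are too few, it is the ELC group.

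Appendix I gives the model. For the non-ICE route at Month 6, logistic regression "will be used in the MI procedure with model factor randomization stratum (history of MAC lung infection, initial or subsequent"; the ICE route also has randomized treatment. For Month 7 the same approach is used with one addition: "Model will additionally include culture conversion status by Month 6 (possibly imputed) as additional model factor".

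**The concern.** The added predictor is conversion by Month 6, which needs two negative cultures. The Month 7 endpoint depends on the Month 6 culture alone plus Month 7. The two disagree for a subject who is positive at Month 5 and negative at Month 6.

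If that subject has no Month 7 culture, one further negative result would make the subject a converter. The model borrows the rate from all non-converters by Month 6, including everyone with a positive Month 6 culture, whose Month 7 status was settled before Month 7 was read. The SAP calls this consistent with missing at random, but an observed predictor that partly defines the endpoint is left out. At stake is a downward push on the reported Month 7 conversion proportion in each arm.

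**Working it through.** **Rule trace for Month 5 positive, Month 6 negative, Month 7 missing**

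1. Month 6 status: not converted (Section 9.3.1.1). Rule 4 of Section 9.3.1.2.1 does not apply, since it covers a missing Month 5 or 6 and needs a negative Month 7.
2. Month 7 converter? No; that needs a negative Month 7 culture (Section 11.3).
3. Month 7 non-converter? No; Month 6 is not positive and Month 7 is absent (Section 11.3).
4. So status is imputed (Section 11.3.1.1), with MAC history and Month 6 conversion status as factors on the non-ICE route (Appendix I).
5. The reference subjects at the same factor level are Month 5 positive / Month 6 negative subjects with Month 7 observed, plus every Month 6 positive subject, with or without a Month 7 culture. The second group contributes only non-conversions.

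This needs no assumed rate: any subject who needs Month 7 imputation and has an observed Month 6 culture is Month 6 negative.

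**Size**

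The plan states no figure to reproduce. Inputs from SAP Section 4.3.1: 50 per arm; conversion c = 50, 60, 70%; missing data m = 5, 20%. Those are planning values for the QOL-B power calculation, borrowed here as ranges for conversion by Month 6 and for a missing Month 7 culture. Assumed, not in the documents: a constant monthly hazard of turning and staying negative over Months 1–5, and q, the chance of a negative Month 7 after Month 5 positive / Month 6 negative, of 0.7–0.9 (0.8 in the table). All subjects are treated as completers with Month 6 observed.

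- Hazard: h = 1 − (1 − c)^(1/5)
- First negative at Month 6, per arm: L = 50(1 − c)h
- Month 6 positive, per arm: P = 50(1 − c) − L
- Month 6 positive share of the reference level: P / [P + L(1 − m)]
- Imputed probability, approximating the logistic fit by the level's observed rate: q × (1 − that share)
- Affected subjects per arm: L × m
- Understatement of the arm's rate: L × m × (q − imputed) / 50

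For c = 60%, m = 5%: h = 0.167, L = 3.35, P = 16.65. Share = 16.65 / (16.65 + 3.18) = 0.840. Imputed = 0.8 × 0.160 = 0.128. Affected = 0.17. Understatement = 0.17 × 0.672 / 50, about 0.22 percentage points.

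| c | m | h | Month 6 positive share | Imputed (target 0.80) | Affected per arm | Understatement (points) |
|---|---|---|---|---|---|---|
| 50% | 5% | 0.129 | 88% | 0.10 | 0.16 | 0.23 |
| 60% | 5% | 0.167 | 84% | 0.13 | 0.17 | 0.22 |
| 70% | 5% | 0.214 | 80% | 0.16 | 0.16 | 0.20 |
| 50% | 20% | 0.129 | 89% | 0.09 | 0.65 | 0.93 |
| 60% | 20% | 0.167 | 86% | 0.11 | 0.67 | 0.92 |
| 70% | 20% | 0.214 | 82% | 0.14 | 0.64 | 0.84 |

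Over q = 0.7–0.9 the understatement runs from 0.18 to 1.04 points. A simulation of 400,000 subjects per conversion rate, at 20% missing and q = 0.8, gave imputed rates of 0.085, 0.109 and 0.143 against an actual rate of about 0.80.

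The Month 6 positive share falls below half only if more than about half of those not yet converted turn negative exactly at Month 6. A constant hazard of 0.5 would mean 1 − 0.5^5 = 97% already converted by Month 5.

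**Alternatives, same assumptions, with 90% of Month 6 converters staying negative**

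- Reference set restricted to Month 6 negative subjects, Month 6 conversion status kept: about 0.80, the target.
- Month 6 culture in place of conversion status: at c = 60%, (30 × 0.9 + 3.35 × 0.8) / 33.35 = 0.89. This overshoots because it pools single-negative subjects with established converters.

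**The case against.** **Little rests on this endpoint.** Conversion by Month 7 is not a protocol endpoint; it appears under other efficacy assessments in the SAP, and Section 7.2 calls all such statistics nominal. With 50 per arm and 60% converting, the 95% half-width is 1.96 × √(0.24/50), about 14 points, for one arm, and 1.96 × √(0.48/50), about 19 points, for the difference. A shift of up to about 1 point is small beside either. This stands and limits the weight of the point.

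**The count may be too high.** The pattern needs Month 6 observed and only Month 7 missing, whereas many who leave early lack both. After conversion, an isolated broth positive or a non-productive visit counts as negative (Section 9.3.1.1), so some apparent Month 5 positives are Month 6 converters. This stands too.

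**The target is not known.** Carrying an assumed on-treatment reversion of 5–15% a month into Month 7 would give 85–95%. But Month 7 is off treatment by design, the subject has a single negative culture after a positive one, and a non-productive Month 7 before conversion counts as positive. The documents give no rate; hence the assumed 70–90%.

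**Stronger readings.** A reader might infer that proven late converters are being scored as failures. They are not proven: without Month 7 they are undetermined. A reader might also infer a biased treatment comparison. No document figure shows late conversion or missing Month 7 cultures differing by arm; if they are similar, the effect largely cancels.

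**Where the mechanism is uncertain.** If the ELC reference group is used, Appendix I lists only MAC history for conversion, so it is unclear whether the Month 6 factor stays. If Month 5 is missing rather than positive, Month 6 status is itself imputed and the problem arises only in draws that give non-conversion. Parts of Appendix I are redacted; the trace uses only the readable factors.

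None of this supplies a rule that separates the Month 6 negative subject from the Month 6 positive reference subjects.

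**Conclusion.** The pooling is wrong as written and follows from the SAP's own definitions. A subject with an observed negative Month 6 culture, no conversion by Month 6 and no Month 7 culture takes the rate of a group that includes subjects already ruled out. That Month 6 positive subjects are the large majority of the group, and that the imputed probability is far too low, is an inference from the assumptions above.

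The practical effect is small: under one expected subject per arm, and an understatement of about 0.2–1 percentage point in an arm's Month 7 proportion. The primary objective and the Month 6 conversion endpoint are untouched. The correlations in Section 11.4 are not multiply imputed and are also untouched. This is an inexpensive refinement, not a threat to the study's conclusions.

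**What to change.** In Appendix I (imputation of conversion status by Month 7) and Section 11.3.1.1, add that for a subject with an observed negative Month 6 culture and no Month 7 culture, the reference set on the same route is restricted to subjects with an observed negative Month 6 culture. Keep conversion by Month 6 as a factor where the cell supports it. Keep the present model where the Month 6 culture itself is missing.

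If the ICE retriever set is too small after this restriction, apply the same restriction within the ELC reference group already planned, and state whether the Month 6 factor stays in that model. The blinded data review meeting, which already decides on the ELC fallback, is the place to settle cell sizes.

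The cost is a short SAP change and a revised reference flag, with smaller cells and somewhat more variable imputations. Under the assumptions above, only L(1 − m), about 2.6–3.2 subjects per arm, are Month 5 positive / Month 6 negative with Month 7 observed; the ICE route would have fewer. If Month 6 status then has to be dropped, the restricted set gives about 0.89 against 0.80. That is too high, but far closer than 0.09–0.16.

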**Imputation of PRO and conversion data based on ELC reference group**

In case that the retriever group will be too small to use, the reference group will be subjects from ELC group. Final determination will be made at the time of BDRM.

Specifically, NMAR imputation will be based on those subjects from ELC group who have Month 7 data (including retrievers and subjects experiencing ICE). Imputation model will include (history of MAC lung infection, initial or subsequent), additionally, imputation of PRO change from baseline to Month 7 will include baseline PRO in the MI model.

MAR imputation will be based on those subjects from ELC group who stayed in the study and have Month 7 data.

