## **7.4. Handling of Missing Data**

The handling of missing data and appropriate imputations described in the following sections will be performed after all efforts fail to obtain the data.

If appropriate, retrieved data will be used. A retrieved assessment is one collected after the early discontinuation of ALIS/ELC; a retriever is a subject who stays in the study and continues to provide data after discontinuation of the randomized treatment regimen.

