Justification for the rule: In most cases, physicians caring for patients discontinuing ALIS/ELC due to an ICE will elect to continue AZI and ETH alone or provide an alternative regimen in order to complete an adequate period of treatment for MAC lung infection. In case of an AE leading to ICE, treatment options for MAC lung disease known to be efficacious other than (at a minimum) the combination of a macrolide plus ethambutol already provided in the study are limited. Furthermore, for ICE patients requiring “rescue therapy” as defined in protocol Section 5.2.2 (ie, a change from randomized treatment due to progression of MAC lung infection), these patients are failing initial course of therapy and should be considered refractory; recommended treatment in that case would be the addition of ALIS – which may or may not have been the cause of the ICE. Therefore, subjects experiencing an ICE are expected to have a microbiologically worse outcome due to limited treatment options following the ICE, and imputation of PROs to the retriever distribution is more representative of their clinical outcome.

- For subjects not experiencing ICE, their missing Month 6 conversion status will be imputed based on the observed status distribution from the subjects who completed 6 months of randomized treatment, have Month 6 conversion status determined, and were randomized to the same treatment group. This approach is consistent with MAR approach imputation.

The ELC treatment group (including retriever) will be used instead if the ICE retriever subgroup is too small to allow imputations as described above. The decision as to which group will be used in the imputation will be determined prior to unblinding at the blinded data review meeting.

Imputation details are included in the [Appendix I](#).

### 9.3.2. QOL-B Patient-reported Respiratory Symptoms at Month 7

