### 9.3.2.2.1. Data Handling

For the purpose of the analysis the influence of ICEs and the presence of the missing data on the estimation of change from baseline to Month 7 PRO means will be taken into consideration. The ICEs are defined as post-randomization events leading to early ALIS/ELC therapy termination due to death, ALIS/ELC-related TEAE, use of rescue medication, or lack of efficacy.

Change from baseline to Month 7 will incorporate the following considerations:

1. A subject who dies after randomization will be assigned the worst observed change score in the entire sample as the change from baseline to Month 7
2. Retrieved Month 7 assessments will be used in the analysis, ie, collected after early termination of ALIS/ELC (see [Section 7.4](#) for definition)
3. Data for subjects who complete 6 months of the randomized treatment however their Month 7 PRO is not available will be imputed based on the observed status distribution from the subjects who completed 6 months of randomized treatment (ALIS/ELC, AZI and ETH), have Month 7 available, and were randomized to the same treatment group. This approach is consistent with MAR approach.
4. When retrieved assessments are unavailable the missing change from baseline to Month 7 will be imputed as follows:
  - For subjects experiencing ICEs other than death, their missing Month 7 PRO will be imputed based on the retrieved assessment distribution from those retrievers who experienced ICE and are exposed to an altered treatment regimen after their ICEs. MNAR imputation of the data for those subjects experiencing ICE is applied.

Justification for usage of retrievers' data is included in [Section 9.3.1.2.1](#).

- For subjects not experiencing ICE, their missing Month 7 PRO data will be imputed based on the observed data distribution from the subjects who completed 6 months of randomized therapy (ALIS/ELC, AZI and ETH), have Month 7 PRO data assessment available, and are randomized to the same treatment group. This approach is consistent with Missing-at-Random (MAR) approach.

Imputation details are included in [Appendix I](#).

The ELC treatment group will be used instead if the ICE retriever subgroup is too small to allow imputations as described above. The decision as to which group will be used in the imputation will be determined prior to unblinding at the data review meeting.

The results of the analyses for each imputation will be combined using Rubin's rule.

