#### Imputations for subjects not experiencing ICE and whose retrieved assessments at Month 7 are unavailable

For subjects not experiencing ICE, their missing Month 7 PRO change from baseline will be imputed based on the observed data distribution (flagged as Ref\_MAR) of subjects who completed 6 months of randomized therapy, have Month 7 PRO data assessment available, and are randomized to the same treatment group. This approach is consistent with MAR approach.

The missing data will be multiply imputed using PROC MI in SAS. The Sponsor believes that multiple imputation method is appropriate to appropriately estimate the mean and variance of the treatment effect. Fifty replications are sufficient to reflect variability of the imputations. The variables used in the MI model (predictors) will be randomization stratum (history of MAC lung infection, initial or subsequent) and PRO score at baseline. [REDACTED]

Imputations for subjects completing randomized therapy and whose assessments at Month 7 are unavailable

Data for subjects who complete 6 months of the randomized treatment however Month 7 PRO assessment is not available will be imputed based on the observed distribution from the subjects who completed 6 months of randomized treatment, have Month 7 PRO assessment, and were randomized to the same treatment group. This approach is consistent with MAR approach imputation. The missing data will be multiply imputed using PROC MI in SAS as described above.

Analysis methods

[REDACTED]

The ANCOVA analysis as specified in [Section 9.3.2.2](#) will be performed using each of the 50 full sets. The 50 sets of results will be then combined using Rubin's rule implemented via SAS PROC MIANALYZE with the specification of their effect estimates together with the corresponding standard errors, resulting in a single set of estimates and testing statistics for the treatment effect.

**Culture conversion imputations**Imputations for subjects who experienced ICE (other than death) and whose retrieved Month 6 conversion status is unavailable.

For subjects experiencing ICEs other than death, their missing Month 6 conversion status will be imputed based on the retrieved assessment distribution (flagged as Ref\_MNAR) from those retrievers who experienced ICE and are exposed to an altered treatment regimen after their ICEs. This approach is consistent with MNAR methodology.

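### When the ICE-retriever group is too small, SAP Appendix I also moves the MAR donors to the ELC arm, against the SAP's own same-arm rule; a smaller gap is that the Month 6 conversion rules lack a known-positive rule

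*SAP*

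**What the plan says.** **MAR donors.** SAP 9.3.1.2.1, 9.3.2.2.1, 11.3.1.1 and Appendix I agree. Two kinds of subject, those who stopped early without an ICE and those who finished treatment but lack the endpoint, are imputed from completers of their own arm. For the Month 7 PRO, Appendix I takes donors "who completed 6 months of randomized therapy, have Month 7 PRO data assessment available, and are randomized to the same treatment group"; 9.3.2.2.1 says the same. For Month 6 conversion, Appendix I requires donors to "have Month 6 conversion status available, and are randomized to the same treatment group".

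**ICE donors.** Subjects with an ICE other than death are imputed from retrievers who had an ICE. SAP 7.4 explains that "a retriever is a subject who stays in the study and continues to provide data after discontinuation of the randomized treatment regimen".

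**Fallback.** In 9.3.1.2.1 the ELC group "will be used instead if the ICE retriever subgroup is too small to allow imputations as described above". Sections 9.3.2.2.1 and 11.3.1.1 give the same trigger, and the choice is made at the blinded data review. The last subsection of Appendix I starts from that trigger and moves the ICE (MNAR) branch to ELC. It then adds: "MAR imputation will be based on those subjects from ELC group who stayed in the study and have Month 7 data".

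**Month 6 conversion.** SAP 9.3.1.1 states: "The secondary endpoint culture conversion by Month 6 is defined as MAC culture negative at Month 5 and Month 6". It also states: "A non-productive assessment will be considered culture positive if the assessment occurs prior to culture conversion or post recurrence". In 9.3.1.2.1, the justification of rule 4 treats the status as indeterminate when either visit is missing. Rules 5 and 6 then impute what rule 4 has not resolved. For the Month 7 endpoint, 11.3 expressly makes a positive culture at Month 6 or Month 7 a non-conversion.

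**The concern.** The fallback is a remedy for too few ICE retrievers. The MAR branch does not use retrievers, so nothing in the trigger makes its donors unavailable. Appendix I moves them anyway and gives no reason. An ALIS subject who left without an ICE, or who finished treatment and missed one assessment, would then get values typical of the comparator arm. That is a reference-based assumption carrying the MAR label, and it draws the arm difference towards zero.

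The same sentence identifies donors by their Month 7 data, although the subsection heading covers conversion as well. Under the fallback, donors for the Month 6 conversion endpoint are therefore not properly defined.

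The second, smaller matter is that two programmers could derive different Month 6 conversion rates from the same data. One would apply the endpoint definition and call a known positive a non-converter. The other would follow the rule 4 justification and impute.

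**Working it through.** The SAP gives no figure for either point. The nearby statement of at least 80% power (SAP 4.3.1) concerns converters against non-converters and is not affected.

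**Point 1: the passages side by side**

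| Branch | Default donors | Uses retrievers? | Donors under the Appendix I fallback |
|---|---|---|---|
| ICE other than death | ICE retrievers | Yes | ELC subjects with Month 7 data |
| Early stop without ICE | Own-arm completers | No | ELC subjects with Month 7 data |
| Completer, endpoint missing | Own-arm completers | No | ELC subjects with Month 7 data |

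Only the first row depends on the size of the retriever group.

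**Point 1: size**

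Inputs: 50 subjects per arm (SAP 4.3.1), and k ALIS subjects in rows two and three, a number the documents do not give. Let D be the difference that own-arm imputation would estimate.

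- Expected ALIS mean with ELC donors = [(50 − k) × ALIS mean + k × ELC mean] / 50.
- Expected difference = D × (1 − k/50).
- k = 1: 1/50 = 2% of D is lost.
- Equal missingness by arm, at the 5% and 20% assumed for the power statement: k is at most 0.05 × 50 = 2.5 or 0.20 × 50 = 10, so the loss is at most 5% or 20%. These totals include deaths and ICE subjects, so the real share would be lower.
- All missing subjects in the ALIS arm: 0.05 × 100 = 5 or 0.20 × 100 = 20, giving limits of 5/50 = 10% and 20/50 = 40%.

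Illustration with assumed differences: 7 points becomes 7 × 0.95 = 6.65 or 7 × 0.80 = 5.6. Conversion of 70% against 50%, a gap of 20 percentage points, becomes 19 or 16. The planning rates were set for the QOL-B simulation; using them for cultures is a further assumption.

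**Point 2: one subject followed through the rules**

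Take a subject with Month 5 missing and Month 6 classified positive.

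- Endpoint definition (9.3.1.1): both visits must be negative, so the subject fails.
- Rule 4 (9.3.1.2.1): it can only assign converters, and this subject does not qualify.
- Justification of rule 4: one visit is missing, so the status is treated as unknown.
- Rules 5 and 6: an unknown status is imputed and can come out as conversion.
- Section 11.3: the same Month 6 culture makes the subject a certain non-converter by Month 7.

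If such a subject is imputed with donor conversion rate q, the arm's expected rate rises by 100 × q / 50 percentage points. For q = 0.3, 0.5 and 0.7 this is 0.6, 1.0 and 1.4. The 50% and 70% are planning rates from SAP 4.3.1. The 30% is an assumed lower case, because both late visits must be negative. The number of such subjects is not known.

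**The case against.** **On point 1.** The fallback is declared in advance, its use is decided before unblinding, and it may never be triggered. In 9.3.1.2.1 and 9.3.2.2.1 the fallback sentence follows both the ICE and the non-ICE bullets, so it could be read as covering both. Borrowing from ELC is usually the conservative direction, and SAP 7.2 disclaims inference from these comparisons. All of this limits the importance of the point, but the inconsistency remains. The body text substitutes ELC for the retriever subgroup, which only the ICE bullet uses. A conservative analysis can be defended, but it is not the same-arm MAR approach that the SAP describes. If the sentence was meant only for ELC subjects' own missing values, it needs to say so.

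**On point 2.** The endpoint definition already fails a subject with an observed positive, and a careful programmer would apply it. That is why this is minor. A fix must also respect the rule in 9.3.1.1 that a lone broth-positive visit after conversion counts as negative.

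**Stronger readings that the documents do not support.**

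- A reader might infer that using ELC for ICE subjects is itself an error. It is a declared alternative.
- A reader might infer that the looser donor description, staying in the study, lets retrievers into the MAR pool. The preceding sentence names retrievers and ICE subjects for the MNAR branch only, which points the other way.
- A reader might infer that the PRO imputation model wrongly omits the Month 6 score. Redacted text directly follows the predictor list in Appendix I, so the full model cannot be judged.
- A reader might infer that the psychometric validation is compromised. Its methods are in the Validation Analysis Plan, which is not among these documents.

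**Conclusion.** Point 1 holds: the MAR sentence in the last subsection of Appendix I is wrong as written, because it changes donors that the trigger does not concern and contradicts the own-arm rule stated elsewhere in the SAP. It applies only if the fallback is used. The loss is about 2% of the expected arm difference per affected ALIS subject, assuming 50 per arm and that own-arm MAR would have been right. The 5% and 20% limits hold only with equal missingness by arm; concentration in ALIS raises them.

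Point 2 holds as a minor gap in wording. Each affected subject would add roughly 0.6 to 1.4 percentage points to an arm's Month 6 conversion rate under the assumed donor rates. The arm difference moves only if the number of such subjects or the donor rate differs between arms.

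Both concern secondary comparisons with nominal p-values, and 9.3.2.2 notes that the PRO comparison is not powered.

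**What to change.** 1. In the last subsection of Appendix I, limit the ELC fallback to the ICE (MNAR) branch. State that subjects without an ICE, and completers with a missing endpoint, stay imputed from completers of their own arm. Define donors for Month 6 conversion by available Month 6 conversion status, not by Month 7 data.
2. In 9.3.1.2.1, add that a Month 5 or Month 6 visit classified as MAC positive makes the subject a Month 6 non-converter, once the single-broth-positive rule and the non-productive rule have both been applied. Impute only when no such positive is observed, and align the justification of rule 4 with this.

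Both are changes of wording. They need no new data and no new model, and should be settled before the blinded data review at which the fallback is decided.
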